6.5.3 Post-study medications

Post-study treatment will be in accordance with institutional protocol and best practice.

6.6 Treatment compliance

AZD9773 and placebo infusions will be administered by the investigator or medically qualified personnel in a medically monitored setting. The times and dates of the AZD9773 and placebo doses will be recorded in the eCRF.

6.6.1 Accountability

The study drug provided for this study will be used only as directed in the study protocol.

The study personnel will account for all medications dispensed and returned.

It is the study centre's responsibility to establish a system for handling study drugs, including IPs, so as to ensure that:

- Deliveries of such products are correctly received by a responsible person (eg, a pharmacist) and are recorded
- Study drug is handled and stored safely and properly
- Study drug is administered only to study patients in accordance with the protocol

- Unused study drug and empty containers are destroyed at the centre or through a destruction vendor after appropriate monitoring
- Certificates of delivery and return are signed, preferably by the investigator or a pharmacist, and copies retained in the investigator file.

At the end of the study, it must be possible to reconcile delivery records with records of study drug use and destroyed/returned stock.

Study drug will be dispensed to the investigator or medically qualified personnel by the site pharmacist. The IPs will be administered to patients only by the investigator or medically qualified personnel named on the form of the Food and Drug Administration-1572 for sites in the USA, or as documented per local requirements in the clinical study agreement (CSA). Records of study drug usage should include the identification of the person to whom the study treatment was administered, the quantity and date of administration, and a record of unused study drug. The investigator/pharmacist is responsible for maintaining accurate study drug accountability records throughout the study on the relevant forms provided by AstraZeneca or PAREXEL. Each administration of study drug will be documented in the eCRF.

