6.3 Blinding and procedures for unblinding the study

6.3.1 Methods for ensuring blinding

The study will be performed in a double-blind manner. The patient, the investigator and study centre staff will be blinded to study drug allocation. The study centre pharmacist will be unblinded to study drug and will prepare AZD9773 or placebo for a patient as specified by the randomisation scheme and IVRS (pharmacists will call into IVRS to obtain the randomisation/treatment allocation details). All study drug will be blinded using an opaque sleeve, fastened with tamper-evident tape over the iv bag prior to dispensing to other study personnel to maintain the double-blind conditions. Pharmacists will be given specific instructions for study drug preparation and will note if the double-blind conditions have been compromised or the blind broken. All loading doses will be made up to a volume of 250 mL and all maintenance doses will be made up to a volume of 100 mL. Lot numbers of AZD9773 dispensed will be recorded by the pharmacist and monitored by an unblinded monitor. Other study centre staff and monitors will not be given access to lot number information.

Procedures in the case of unblinding by the investigator or designee are described in Section [6.3.2](#).

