6.4 Treatments

6.4.1 Identity of investigational product(s)

Details of the investigational study drug are provided in Table 3. Further information on AZD9773 can be found in the current IB. Doses will be prepared by a pharmacist unblinded to study treatment as specified in the Pharmacist Handling Instructions. All study drug will be blinded using an opaque sleeve, fastened with tamper-evident tape over the iv bag prior to dispensing to other study personnel.

Table 3 **Investigational product**

Investigational product	Dosage form and strength	Manufacturer	Formulation number
AZD9773	5000 units of AZD9773 lyophilised powder/vial for reconstitution in saline and dilution in saline for iv infusion (dose is dependent on treatment arm)	[REDACTED]	F13605
Active Component	AZD9773 (rh TNF α immune Fab [ovine]) [REDACTED]		
Excipients	Di-sodium hydrogen phosphate, USP, Ph Eur Sodium chloride, USP, Ph Eur		
Placebo	0.9% sodium chloride		Not applicable

Vials of AZD9773 will be supplied by AstraZeneca or an AstraZeneca designee to each centre. Study centres will be supplied with sufficient AZD9773 for the study.

Prior to use, AZD9773 must be reconstituted with saline. For iv loading infusions, the reconstituted solution will be diluted to 250 mL of saline solution. For all iv maintenance doses, the reconstituted solution will be diluted to 100 mL of saline solution.

Placebo

Placebo will be saline solution (0.9% sodium chloride) administered as an iv infusion in an equivalent volume to the active treatment (volume of 250 mL for the loading dose and 100 mL for maintenance doses). The pharmacy at each study centre will supply saline for the study.

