6.4.2 Doses and treatment regimens

During the treatment period, patients will receive AZD9773 250/50 units/kg or AZD9773 500/100 units/kg or placebo. The first dose of study drug should be administered within 24 hours after confirmation of the onset of qualifying organ failure resulting in severe sepsis and/or septic shock (see Section 5.1 for further details on inclusion criteria). Study drug will be administered by iv infusion.

Each infusion in all treatment arms will be administered over a 30-minute period. Medical management of infusion reactions is detailed in [Appendix D](#). AZD9773 and placebo will be

administered by the investigator or medically qualified personnel in a medically monitored setting. The dose, infusion time and volume remaining for each dose will be recorded in the eCRF together with the date and time of administration (using 24:00-hour clock).

If vasopressors are required during the loading dose, the following should be recorded from 2 hours before the loading dose, during the loading dose and until 30 minutes after completion of the loading dose: name of drug, start date and time, dose, all interim rate changes during administration, route of administration, stop date and time. This applies only to the loading dose.

The body weight measured at screening, measured as close as possible to the first dose but within 24 hours before the first dose, will be the body weight used for all dose calculations during the study. The maximum dose given is based on a 100 kg body weight. If a patient weighs >100 kg, he or she will be given the maximum dose. See [Appendix D](#) for more detailed guidance on handling tolerability.

The last dose may be on Day 5 or Day 6 depending on the start time of the loading dose on Day 1. Dosing should not continue past Day 6.

If necessary, a one-time dosing interval adjustment can be made after the loading dose to create a suitable morning/evening schedule 12 hours apart. The dosing interval adjustment must be such that the first maintenance dose is given a minimum of 6 hours and a maximum of 15 hours after the loading dose. Dosing can be discontinued before all 10 doses are administered if the patient improves and maintains improvement for 24 hours. Improvement is defined as a patient no longer requiring haemodynamic or ventilatory support, no longer requiring ICU admission and there is no evidence of worsening organ failure for at least 24 hours.

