10.3 Monitoring of the study

During the study, a PAREXEL representative will have regular contacts with the study site, including visits to:

- Provide information and support to the investigator(s).
- Confirm that facilities remain acceptable.
- Confirm that the investigational team is adhering to the protocol that data are being accurately and timely recorded in the eCRFs, and that IP accountability checks are being performed.
- Perform source data verification (a comparison of the data in the eCRFs with the patient's medical records at the hospital or practice, and other records relevant to the study) including verification of informed consent of participating patients.

Investigators must allow direct access to all original records for each patient (eg, clinic charts).

- Ensure withdrawal of informed consent to the use of the patient's biological samples is reported and biological samples are identified and disposed/destroyed accordingly, and the action is documented, and reported to the patient.

The PAREXEL representative will be available between visits if the investigator(s) or other staff at the centre needs information and advice about the study conduct.

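### Section 6.6.1 lets the blinded investigator keep accountability records that can reveal the treatment arm, while the access bar in 6.3.1 covers lot numbers only

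*Protocol*

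**What the plan says.** Section 6.3.1 sets the blind: "The patient, the investigator and study centre staff will be blinded to study drug allocation". The site pharmacist is the exception; he or she obtains the allocation from the IVRS and prepares each bag. The pharmacist also records the lot numbers dispensed, and an unblinded monitor checks them. Other site staff and monitors are kept from lot numbers. No other pharmacy information is named in that bar.

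Section 6.6.1 covers accountability. It gives responsibility for the records to a joint role: "The investigator/pharmacist is responsible for maintaining accurate study drug accountability records throughout the study". Usage records identify the patient and show "the quantity and date of administration, and a record of unused study drug". Stock must balance: "it must be possible to reconcile delivery records with records of study drug use and destroyed/returned stock". On deliveries and returns it says: "Certificates of delivery and return are signed, preferably by the investigator or a pharmacist, and copies retained in the investigator file".

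Section 6.4.1 gives the active product as "5000 units of AZD9773 lyophilised powder/vial" and has each site pharmacy supply the saline used as placebo. Section 6.2 has the investigator pass the patient's weight to the pharmacist. Section 6.4.2 adds an eCRF item: "The dose, infusion time and volume remaining for each dose will be recorded in the" eCRF. It does not say who records it, or whether the dose entry is a dose number or a number of units.

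**The concern.** The two sections do not fit together. One blinds the investigator; the other permits the same person to keep, sign and file records from which the allocation can be worked out. The lot-number bar does not close this route, because the informative item is the amount of AZD9773 used for a patient, not its batch.

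Elsewhere the protocol guards against this kind of leak. Section 6.4.3 keeps the batch number off the bag cover, and section 11 withholds PK data until database lock because they would unblind the study. Patient-level drug quantities get no such protection.

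Much of what the trial measures depends on site judgement. The clinical team decides on extubation (Appendix H), which drives ventilator-free days, the primary endpoint. The investigator decides whether ICU care was needed on a given day (7.6.9), whether a death was clearly due to sepsis (7.3.2) and whether an adverse event was drug-related (7.3.3). Knowing the arm could bias any of these.

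**Working it through.** **Inputs, all from the protocol.** Vial strength is 5000 units (6.4.1, Table 3). The loading dose is 250 or 500 units/kg and the maintenance dose 50 or 100 units/kg, with up to 9 maintenance doses and dosing weight capped at 100 kg (4.1). Placebo uses no vials (6.4.1). **Assumption, not in the protocol:** whole vials are opened for each dose and not shared between doses or patients.

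**Check against the plan's own figures.** At the 100 kg cap, the loading doses are 250 × 100 = 25000 and 500 × 100 = 50000 units. The maintenance doses are 50 × 100 = 5000 and 100 × 100 = 10000 units. All four match the stated maxima.

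**Formula.** Vials per dose = units/kg × min(weight, 100) ÷ 5000, rounded up. Course total = loading vials + 9 × maintenance vials.

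**Worked case, 70 kg.**
- Dose arm 1: loading 17500 ÷ 5000 = 3.5, so 4 vials; maintenance 3500 ÷ 5000 = 0.7, so 1 vial; course 4 + 9 × 1 = 13.
- Dose arm 2: loading 35000 ÷ 5000 = 7 vials; maintenance 7000 ÷ 5000 = 1.4, so 2 vials; course 7 + 9 × 2 = 25.
- Placebo: 0 throughout.

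| Weight (kg) | Loading, arm 1 / arm 2 | Each maintenance dose, arm 1 / arm 2 | Full course, arm 1 / arm 2 |
|---|---|---|---|
| 40 | 2 / 4 | 1 / 1 | 11 / 13 |
| 50 | 3 / 5 | 1 / 1 | 12 / 14 |
| 60 | 3 / 6 | 1 / 2 | 12 / 24 |
| 70 | 4 / 7 | 1 / 2 | 13 / 25 |
| 80 | 4 / 8 | 1 / 2 | 13 / 26 |
| 90 | 5 / 9 | 1 / 2 | 14 / 27 |
| 100 or more | 5 / 10 | 1 / 2 | 14 / 28 |

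**What a quantity reveals.**
- Active versus placebo: always clear from the count, since placebo is 0 and any active dose takes at least one vial.
- Which active arm, weight known: always clear from the loading count. At every whole-kilogram weight from 30 to 160 kg the two arms need different numbers of vials.
- Which active arm, weight unknown: not always clear. From 40 kg upward, arm 1 loading counts run from 2 to 5 and arm 2 counts from 4 to 10, so 4 and 5 occur in both. Four vials fit arm 1 at 70 kg or arm 2 at 40 kg.
- Maintenance counts separate the active arms only above 50 kg.

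The investigator supplies the weight, so the third case offers little protection.

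**Volume.** Bags are made up to 250 mL (loading) or 100 mL (maintenance) in every arm (6.3.1), so a residual or infused volume says nothing about the arm.

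**The case against.** The strongest reply is that the two sections can be read together. Section 6.6.1 names alternatives, and the pharmacist satisfies each of them. The pharmacist is already unblinded, prepares and dispenses every dose, and is the section's own example of who receives deliveries. A site that reads the slash as pharmacist only complies with both sections and its blind holds. That is right, and a reader who concludes that the site blind must fail goes further than the text. What remains is that the opposite reading is equally permitted, at about 100 centres, and nothing in 6.3.1 forbids it.

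Other strong readings also need limiting:

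- A reader might infer that a vial count by itself always identifies the arm. It does so for active versus placebo; separating the active arms can require the weight.
- Section 6.6.1 asks for a quantity without saying vials, and the forms are not shown. The stock reconciliation requirement makes vials or units the natural entry, but this is an inference.
- Delivery and return certificates are stock documents. A signature on one does not by itself disclose any patient's arm. Their place in the investigator file matters mainly alongside the usage records.
- A reader might infer from 6.4.2 that bedside staff must open the sealed sleeve to read the volume left, or must enter units. The sentence names no recorder, the sleeve's construction is not described, and the dose entry is undefined. Volume is the same in all arms, and nothing says that the solutions look different. Only the undefined dose entry deserves clarification, because the exposure summary in 13.3.9.1 needs units/kg and units with a known weight would show the arm.
- A reader might take section 10.3 to send a blinded monitor through the accountability log. It asks the CRO representative only to confirm that "IP accountability checks are being performed", which does not require seeing patient-level quantities.

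**Conclusion.** The point holds as a gap in protection. Section 6.6.1 permits a blinded endpoint assessor to keep records that can disclose allocation, and the bar in 6.3.1 stops at lot numbers. Where such a record is seen, the disclosure is complete: active versus placebo from the count alone, and the dose arm once weight is added (0, 4 or 7 loading vials at 70 kg).

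This rests on whole vials per dose, on quantities being recorded as vials or units, and on a blinded investigator actually seeing a patient-level record. The protocol allows the last of these but does not require it. The documents give no basis for saying how often it would happen or how far any endpoint would shift. No sample-size or power figure is affected. The change is worth making because the endpoints depend on judgement and the remedy uses roles that already exist.

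**What to change.** - **6.6.1:** name the unblinded pharmacist, in place of the joint investigator/pharmacist role, as the person responsible for accountability records, and as the signatory of delivery and return certificates. Keep both in a restricted pharmacy file, not the investigator file, closed to blinded staff until final database lock. Emergency unblinding under 6.3.2 is unaffected.
- **6.3.1:** extend the access bar from lot numbers to all accountability records, and have the unblinded monitor check them.
- **6.4.2:** state that blinded staff record dose number, times and volume infused. Units for the exposure summary in 13.3.9.1 are then derived from the pharmacy log after lock.

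The cost is small: revised wording, minor changes to forms and eCRF instructions, and delegation of accountability sign-off from the investigator to the pharmacist. Both the unblinded pharmacist and the unblinded monitor are already in place under 6.3.1.

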7. COLLECTION OF STUDY VARIABLES

7.1 Recording of data

The investigator will ensure that all data collected in the study are provided to AstraZeneca. He/she ensures the accuracy, completeness, legibility and timeliness of the data recorded in the appropriate sections of the eCRF and according to any instructions provided and of the provision of answers to data queries according to the CSA.

The investigator will provide AstraZeneca with all data produced during the study from the scheduled study assessments. He/she ensures the accuracy, completeness, legibility, and timeliness of the data reported to AstraZeneca in the eCRF and in all required reports.

Data will be entered in the Web Based Data Capture (WBDC) system at the study site. Trained study personnel will be responsible for entering data specified in the protocol into the WBDC system and according to the eCRF instructions. When data have been entered, reviewed, edited and Source Data Verification performed by a PAREXEL representative, the data will be frozen to prevent further editing. The investigator will be notified to sign the eCRF electronically as per the eCRF instructions. A copy of the eCRF data will be archived at the study site.

7.2 Screening and demography procedures

The following screening and demographic data must be collected prior to the first dose of study drug and will be documented in the eCRF (see [Table 1](#) for the timing of these assessments). All times will be recorded using the 24-hour clock.

- Provision of written informed consent by the patient or his/her legally authorised representative. This must be obtained at screening for all patients. Additional written informed consent for participation in the genetic and/or biomarker research is also required for patients willing to participate.
- Confirmation of inclusion and exclusion criteria.
- Date of birth, race/ethnic background, and gender, date and time of admission to ICU, distance of patient's residence from study hospital, details of any transfer from previous hospital to study hospital.
- Medical and surgical history including previous medications (see Section 6.5.1) and concomitant medications, and Charlson Comorbidity Scale (see Section 7.5).
- Physical examination, plus measurement of height, weight (measured as close as possible to the first dose but within 24 hours before the first dose), lung auscultation and a dermal examination (the baseline physical examination at screening must be done within 4 hours before study drug administration) (see Section 7.3.6).
- Blood samples will be collected for:
 - Serum pregnancy test (patients may be entered into the study on the basis of a negative urine pregnancy test, pending the results of a serum pregnancy test; if the serum pregnancy test is positive, the patient must be discontinued from study treatment), unless post-partum.
 - Haematology, clinical chemistry, coagulation parameters, and safety monitoring; samples to be collected within 12 hours prior to start of first infusion (within 6 hours for lactate) (see Section 7.3.5.1).
 - Optional blood sample for biomarker development (see Section 7.8.1). This should be taken at screening within 3 hours prior to the first dose.
 - Optional blood sample for genetic research (see Section 7.8.1). This should be taken at screening but may be taken at any time during the study.
 - Cytokines and chemokines.
 - Plasma renal panel for exploratory analysis.
 - IgE.
- Urine sample (see Section 7.3.5.1):
 - Urinalysis.

- Ventilator use and pulmonary assessment (see Section 7.6.4).
- Vital signs including oximetry (see Section 7.3.8).
- APACHE II score; modified Sequential Organ Failure Assessment (SOFA) score, and Glasgow Coma Score (see Sections 7.6.1 and 7.6.3).
- Daily volume status prior to randomisation.
- AEs.
- Assessment of organ failure (see Section 7.6.5).
- Infection assessment (see Section 7.6.7). The site of infection at screening should be noted. All patients must have a blood culture prior to randomisation. The blood culture result does NOT have to be known prior to randomisation.

7.2.1 Follow-up procedures

The follow-up data will be collected and recorded in the appropriate sections of the eCRF (refer to Study Plan, Table 1). Whether a patient is alive or not at Day 29+2 and Day 90+14, should be recorded in the eCRF (see Table 1). Additionally, the question will be asked “Was aggressive medical care withdrawn?” for those patients who died. For patients discharged from a medical setting, a vendor specialising in home visitation and/or medical aftercare may assist in obtaining follow-up study information according to study procedures.

For HRQoL, the questionnaire may be completed face-to-face or by telephone. Completion of the questionnaire will be interviewer-led.

7.3 Safety

It is of the utmost importance that all staff involved in the study is familiar with the content of this section. The international co-ordinating investigator is responsible for ensuring this.

7.3.1 Definition of adverse events

An adverse event is the development of an undesirable medical condition or the deterioration of a pre-existing medical condition following or during exposure to a pharmaceutical product, whether or not considered causally related to the product. An undesirable medical condition can be symptoms (eg, nausea, chest pain), signs (eg, tachycardia, enlarged liver) or the abnormal results of an investigation (eg, laboratory findings, ECG). In clinical studies, an AE can include an undesirable medical condition occurring at any time, including run-in or washout periods, even if no study treatment has been administered.

The term AE is used to include both serious and non-serious AEs.

Treatment-emergent AEs (TEAEs) (ie, not present at baseline or worsened in severity following start of treatment), including sepsis-related symptoms should be reported as AEs.

7.3.2 Definitions of serious adverse event

A serious adverse event is an AE occurring during any study phase (ie, run-in, treatment, washout, follow-up), and at any dose of the IP or placebo, that fulfils one or more of the following criteria:

- Results in death. All deaths that occur between provision of informed consent and Day 90 must be reported on the statement of death page.
 - Deaths between provision of informed consent and Day 29, if considered unequivocally due to sepsis by the investigator, should **NOT** be reported as a SAE but should be recorded on the statement of death page.
 - Deaths between provision of informed consent and Day 29 if **NOT** considered unequivocally due to sepsis by the investigator should be reported as an SAE as well as on the statement of death page.
 - Deaths between Days 30 and 90 will **ONLY** be reported as a SAE if considered to be related to late-onset toxicity to the study drug by the investigator.
- Is immediately life-threatening.
- Requires in-patient hospitalisation or prolongation of existing hospitalisation.
- Results in persistent or significant disability or incapacity.
- Is a congenital abnormality or birth defect.
- Is an important medical event that may jeopardise the patient or may require medical intervention to prevent one of the outcomes listed above.

For reporting purposes, any suspected transmission via a medicinal product of an infectious agent is also considered an SAE and is reported in an expedited manner. Any organism, virus or infectious particle (for example prion protein transmitting transmissible spongiform encephalopathy), pathogenic or non-pathogenic, is considered an infectious agent.

For further guidance on the definition of a SAE, see [Appendix B](#) to the Clinical Study Protocol.

Note that SAEs that could be associated with any study procedure should also be reported. For such events the causal relationship is implied as “yes”.

